1.4.3 Second evacuation

Second evacuation by ultrasound guided suction curettage is considered to be a safe approach in suitably selected patients. In three contemporary prospective studies recruiting 134 patients with disease recurrence after primary evacuation^{21,22,36}, a total of four grade 1 (3%) and one grade 3 (0.7%; requiring transfusion to support) cases of uterine haemorrhage were observed. In contrast, patients treated with 1st line methotrexate chemotherapy for low risk GTN have a reported rate of grade 3 haemorrhage of approximately 2%³⁷. Amongst patients undergoing second evacuation in the studies noted above, one case of grade 1 uterine perforation (0.7%) was managed conservatively.

RESOLVE	C/43/2022	Imperial College London	v2.0 10 th July 2023
---------	-----------	-------------------------	------------------------------------

2. OBJECTIVES AND ENDPOINTS

2.1 Primary Objectives and Endpoints

Objectives	Endpoints
To determine the feasibility of conducting a definitive study of neoadjuvant pembrolizumab prior to second evacuation of low risk postmolar gestational trophoblastic neoplasia (GTN)	1. The proportion of eligible patients who consent to randomisation. 2. The proportion of patients randomised to the intervention arm who complete protocol treatments.
To collect tissues at the point of second evacuation and blood to support translational research into the mechanisms of immune evasion and immunotherapy sensitivity in this disease	

2.2 Secondary Objective and Endpoint

Objectives	Endpoints
To assess the rate of surgical cure with and without pembrolizumab.	Proportion of patients who achieve a sustained complete response following second evacuation and no further anti-cancer therapy, defined as normalisation of hCG and no rise by 1 year post procedure.
To assess the safety of a single dose of pembrolizumab prior to second evacuation versus second evacuation alone.	Incidence of adverse effects of second evacuation and pembrolizumab within 30 days and 12 weeks respectively, assessed by Common Terminology Criteria for Adverse Events (CTCAE v5.0, 27 Nov 2017).

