5.5 Visit Schedule

Table 2: Schedule of Assessments: Second evacuation only

Procedure	Pre-screening	Baseline/screening Day -3 to 0	Day 7 ¹	2 weeks post evacuation ²	6 weeks post evacuation ²	12 weeks post evacuation ²	Every 2 weeks post evacuation until normalisation of hCG	Every month following normal hCG and until 1 year post evacuation
Informed Consent		X						
Medical History & Demographics		X						
Physical Exam		X		X	X			
Performance Status		X		X	X			
Vital Signs		X						
Haematology	X							
Biochemistry	X							
Coagulation	X							
Viral Screen (Hep B, Hep C, HIV)	X							
Thyroid Function Tests and Cortisol		X						
Tumour marker blood hCG	X						X	
Research Blood Sample		X		X	X	X		
Archival Tissue		X						
Imaging - Chest X-ray	X							
Imaging - Uterine ultrasound scan	X		X					
Randomisation		X						
Surgical evacuation			X					
Urine hCG							X	X
Adverse Events				X	X	X		
Concomitant Medications		X						

RESOLVE	C/43/2022	Imperial College London	v2.0 10 th July 2023
---------	-----------	-------------------------	------------------------------------

1. Visit is permitted to be performed two days prior or after scheduled timepoint.
2. Visit is permitted to be performed three days prior or after scheduled timepoint.

Table 3: Schedule of Assessments: Pembrolizumab arm

Procedure	Pre-screening	Baseline/Screening Day -3 to 0	Day 0	Day +7 ¹	Day +11 ¹	Day +14 ¹	2 weeks post evacuation ²	6 weeks post evacuation ²	12 weeks post evacuation ²	Every 2 weeks post evacuation until normalisation of hCG	Every month following normal hCG and until 1 year post evacuation
Informed Consent		X									
Medical History & Demographics		X									
Physical Exam		X			X		X	X	X		
Performance Status		X			X		X	X	X		
Vital Signs		X			X						
Haematology	X				X			X	X		
Biochemistry	X				X			X	X		
Coagulation	X				X			X	X		
Viral screen (Hep B, Hep C, HIV)	X										
Thyroid Function Tests and Cortisol		X						X	X		
Tumour marker blood hCG	X			X	X					X	
Research Blood sample		X				X	X	X	X		
Archival Tissue		X									
Imaging – Chest X-ray	X										
Imaging – Uterine ultrasound scan	X					X					
Imaging – Optional Magnetic Resonance Imaging			X ³			X ⁴					
Randomisation		X									
Pembrolizumab			X								

RESOLVE	C/43/2022	Imperial College London	v2.0 10 th July 2023
---------	-----------	-------------------------	------------------------------------

Surgical evacuation						X					
Urine hCG										X	X
Adverse Events					X		X	X	X		

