5.7 Follow-up

Following second evacuation, patients in both arms will undergo standard of care urine and blood hCG monitoring every 2 weeks until hCG normalisation and then monthly urine hCG measurement for up to 1 year post evacuation. Failure of second evacuation to result in disease control is defined as per national guidelines (rise or plateau in hCG, hCG over 20,000 IU/L at 4 weeks, heavy vaginal bleeding). Patients will additionally have a clinical review and toxicity check at 2, 6 and 12 weeks post evacuation.

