7.4 Reporting Procedures

All adverse events should be reported. Depending on the nature of the event the reporting procedures below should be followed. Any questions concerning adverse event reporting should be directed to the study coordination centre in the first instance. A flowchart is given below to aid in the reporting procedures.

(i) 7.4.1 Non serious AR/AEs

All such toxicities, whether expected or not, should be recorded in the toxicity section of the relevant case report form and sent to the study coordination centre within one month of the form being due.

(ii) 7.3.2 Serious AR/AEs

Fatal or life threatening SAEs and SUSARs should be reported on the day that the local site is aware of the event. The SAE form asks for nature of event, date of onset, severity, corrective therapies given, outcome and causality (i.e. unrelated, unlikely, possible, probably, definitely). The responsible investigator should sign the causality of the event. Additional information should be sent within 5 days if the reaction has not resolved at the time of reporting.

SAEs

An SAE form should be completed and emailed to the study coordination centre for all SAEs within 24 hours. However, relapse and death due to disease under study and hospitalisations for elective treatment of a pre-existing condition do not need reporting as SAEs.

SUSARs

In the case of suspected unexpected serious adverse reactions, the staff at the site should:

Complete the SAE case report form & send it immediately (within 24 hours,), signed and dated to the study coordination centre together with relevant treatment forms and anonymised copies of all relevant investigations.

[figure not shown]
Or

Contact the study coordination centre by phone and then send the completed SAE form to the study coordination centre within the following 24 hours as above.

The study coordination centre will notify the MHRA, REC and the Sponsor of all SUSARs occurring during the study according to the following timelines; fatal and life-threatening within 7 days of notification and non-life threatening within 15 days. All investigators will be informed of all SUSARs occurring throughout the study.

Local investigators should report any SUSARs and /or SAEs as required by their Local Research Ethics Committee and/or Research & Development Office

Safety Reporting Overview

* Unless identified in the protocol as not requiring immediate reporting

Contact Details for Reporting SAEs and SUSARs:

[contact]

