8.3.4 Safety Analysis

Safety data analysis will be conducted on all subjects randomised within the trial. Data will be collected on the number of patients who are withdrawn from the study in order to commence chemotherapy due to tumour progression. The number and proportion of patients who experience complications arising from second evacuation will be reported. In the intervention arm, the number and percentage of subjects experiencing an AE and the number of events will be reported. Information regarding severity will be examined with a focus on Grade 3-5 events using the Common Terminology Criteria for Adverse Events (CTCAE v5.0).

RESOLVE	C/43/2022	Imperial College London	v2.0 10 th July 2023
---------	-----------	-------------------------	------------------------------------

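### The safety objective compares the two arms, but the endpoint counts only treatment-attributed effects over unequal windows, and the all-AE count is specified for the intervention arm only

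*Protocol*

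**What the plan says.** Section 2.2 of the Protocol words the secondary safety objective as a comparison: "To assess the safety of a single dose of pembrolizumab prior to second evacuation versus second evacuation alone". The only endpoint against it is "Incidence of adverse effects of second evacuation and pembrolizumab within 30 days and 12 weeks respectively", graded by CTCAE v5.0. The trial summary repeats this.

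Data collection is wider than the endpoint. Section 5.7 opens with "Following second evacuation, patients in both arms will undergo standard of care urine and blood hCG monitoring every 2 weeks until hCG normalisation" and continues: "Patients will additionally have a clinical review and toxicity check at 2, 6 and 12 weeks post evacuation". The two schedules in section 5.5, "Table 2: Schedule of Assessments: Second evacuation only" and "Table 3: Schedule of Assessments: Pembrolizumab arm", both mark AEs at those three visits. The pembrolizumab schedule adds one AE check at Day +11, before evacuation. Section 7.4 adds the general rule: "All adverse events should be reported".

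On analysis, section 8.3.4 states: "Safety data analysis will be conducted on all subjects randomised within the trial". It then reports evacuation complications without naming an arm. The number and percentage of patients with an AE, and the number of events, are specified for the intervention arm alone. The sentence on severity, which stresses grades 3 to 5, names no arm.

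**The concern.** A comparison of two randomised arms needs the same kind of event counted over the same period in each. Here the window follows the treatment held responsible for the event. A control patient has only the evacuation, so nothing that happens to her after day 30 can enter the endpoint. An intervention patient has the same 30 days for evacuation effects, plus 12 weeks for whatever is attributed to pembrolizumab.

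An unrelated infection at week 8, for example, would be recorded in both arms. It could count in the intervention arm and could not count in the control arm. Whether it counts is decided by an investigator who knows the allocation. The causality scale in section 7.2 is framed around the trial medication, and that section tells investigators to expect most events to be drug toxicity. Randomisation supplies a control count that would show how many such events occur anyway, but the endpoint leaves it out.

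At stake is whether the trial can answer its own safety objective. Section 1.1 says the results could change standard care or prompt a larger study, so the safety comparison will be read closely despite the small numbers.

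**Working it through.** The Protocol gives no event rate, test or power for safety, so there is no figure of its own to reproduce. The check sets windows against schedules and then illustrates the possible size.

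**1. What is collected, and what is counted**

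| | Control | Intervention |
|---|---|---|
| AE checks after evacuation (5.5, 5.7) | 2, 6, 12 weeks | 2, 6, 12 weeks |
| AE check before evacuation (5.5) | none | Day +11 |
| Evacuation effects counted (2.2) | 30 days | 30 days |
| Pembrolizumab effects counted (2.2) | not applicable | 12 weeks |
| All-AE number and percentage (8.3.4) | not stated | stated |

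Collection after evacuation is equal: 12 × 7 = 84 days in both arms. Evacuation effects also share one window. What differs is the time over which any event can count: 30 days against 84 days, a ratio of 84/30 = 2.8.

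**2. Start of the 12 weeks**

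With the dose on day 0 and evacuation on day 14:
- counted from the dose, the window ends on day 84;
- counted from evacuation, it ends on day 14 + 84 = 98.

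**3. Illustration of size**

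Assume a background AE rate that is constant over time and equal in both arms, and let p be the 30-day incidence. The incidence over 84 days is then 1 − (1 − p)^2.8. The values of p are assumptions; none stands in the Protocol.

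| p at 30 days | Incidence at 84 days | Patients of 10 at 30 days | Patients of 10 at 84 days | Gap |
|---|---|---|---|---|
| 10% | 1 − 0.9^2.8 = 25.5% | 1.0 | 2.55 | 1.55 |
| 20% | 1 − 0.8^2.8 = 46.5% | 2.0 | 4.65 | 2.65 |
| 30% | 1 − 0.7^2.8 = 63.2% | 3.0 | 6.32 | 3.32 |

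These gaps arise only if all-cause events were totalled over 30 days in one arm and 84 in the other, or if every unrelated late event in the intervention arm were attributed to pembrolizumab while all events in the first 30 days count in both. If no unrelated late event is so attributed, the gap from this source is zero.

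**4. Does a common window fit the existing visits?**

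The last AE visit falls at these times:
- Control: day 7 + 84 = 91 (evacuation day in the section 5.5 schedule) or day 10 + 84 = 94 (evacuation day in the trial summary).
- Intervention: day 14 + 84 = 98.

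Taking the permitted margins of 2 days on evacuation and 3 days on follow-up visits, the earliest last visits are day 7 − 2 + 84 − 3 = 86 and day 14 − 2 + 84 − 3 = 93. Day 84 lies within both schedules.

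**The case against.** The best defence is that the windows belong to causes, not to arms. Both arms have the evacuation and share its 30 days. Pembrolizumab effects have no control counterpart under any window, and a longer window for an immunotherapy than for a procedure is reasonable. Section 8.3.4 specifies no between-arm test and no 84-day against 30-day rate. This is a 20-patient feasibility trial with a descriptive safety endpoint, and details of tabulation may sit in an analysis plan that is not shown.

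Much of this stands. The treatment-specific windows are sound as summaries within each treatment. The start of the 12 weeks, taken alone, is a clarification that an analysis plan could supply.

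The defence also disposes of a stronger reading. From the 30-day and 12-week figures, a reader might infer that the arms are observed for different lengths of time and that the intervention arm must look worse by construction. The documents do not support that. AE checks run to 12 weeks post evacuation in both arms, and the endpoint counts effects attributed to a treatment rather than all events. Attribution by an unblinded investigator could also understate pembrolizumab harm.

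What the defence does not meet is the comparative wording of the objective. Cause-specific counts cannot show how many of the events attributed to pembrolizumab would have occurred without it. Nor are the endpoint windows and the restriction of the all-AE count to one arm left open for a later plan: the Protocol states both.

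**Conclusion.** The point holds as a mismatch between objective, endpoint and analysis. Followed as written, the Protocol gives no like-for-like safety comparison: the endpoint rests on attribution with unequal windows, and the all-AE summary is specified for one arm although the data exist for both. The intervention arm can look worse for this reason; it need not.

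The size cannot be fixed from the Protocol. Under assumed 30-day background incidences of 10% to 30%, a constant rate and full attribution of late events to pembrolizumab, the spurious gap would be about 1.5 to 3.3 patients in 10. With no such attribution it is zero. One patient is 10 percentage points of an arm's incidence, so even a single attribution is visible.

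The primary feasibility endpoints are untouched. The change should be made, but it concerns a secondary, descriptive endpoint.

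**What to change.** In the trial summary and sections 2.2 and 8.3.4:

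- Define the comparative safety endpoint as all-cause AEs, any grade and grade 3-5, reported by arm for all randomised patients.
- Use one window for both arms, starting at randomisation and ending on one fixed day that both schedules cover, for example day 84. A window starting at evacuation would drop events between dose and evacuation, and patients withdrawn before evacuation.
- Keep the 30-day evacuation complications (both arms) and the 12-week pembrolizumab-attributed events as descriptive summaries, and state when the 12 weeks start.

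The cost is wording and slightly more tabulation, with no new visits.

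Three limits remain and should be stated with the results:

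- The control arm has no scheduled AE check before evacuation, so its early events rely on the general rule that all AEs are reported.
- The section 5.5 schedules repeat blood tests during the study in the intervention arm only, so laboratory AEs will be found more readily there. Clinical and laboratory events are best shown separately.
- Section 6.11 ends follow-up at withdrawal, while section 9.11 keeps patients given alternative treatment in the study for follow-up. These need reconciling, and the table should show how many patients were not observed to the end of the window.

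The control evacuation day (day 7 in the schedule, day 10 in the summary) also needs reconciling. Day 84 is covered under either.

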3. STUDY DESIGN

3.1 Design

[figure not shown]
This is a single centre, randomised, open-label study of a single dose of 200 mg IV pembrolizumab followed by second evacuation 14 days later, or second evacuation alone for patients with low risk GTN who have failed primary surgical evacuation (Figure 1).

3.2 Treatment regimens

Table 1: Summary of treatment groups

Treatment arm	Number of participants
Second evacuation alone (control)	10
Pembrolizumab followed by second evacuation (Intervention)	10
Total number of participants	20

Figure 1: Study Flowchart

Key:

CHM – Complete Hydatidiform mole; **1ry** – Primary; **CPI** – Checkpoint inhibitor; **Pembro** – Pembrolizumab; **FU** – Follow up Visit

**Complete abstinence (defined as refraining from heterosexual intercourse) must be in line with the preferred and usual lifestyle of the participant. Periodic abstinence (calendar, symptothermal, post-ovulation methods), withdrawal (coitus interruptus), spermicides only, and lactational amenorrhoea method (LAM) are not acceptable methods of contraception. Female condom and male condom should not be used together.*

(ii) Exclusion criteria

1. Patients with other invasive malignancies, with the exception of non-melanoma skin cancer, patients who have had any evidence of the other cancer present within the last 2 years or patients whose previous cancer treatment contraindicates this protocol therapy.
2. Patients with histologically confirmed choriocarcinoma, placental site trophoblastic tumor (PSTT) or epithelioid trophoblastic tumor (ETT) on the first curettage.
3. Pregnant women.
4. Uncontrolled vaginal bleeding.
5. Administration of live vaccine within 30 days prior to the first dose of study drug. Examples of live vaccines include, but are not limited to, the following: measles, mumps, rubella, varicella/zoster (chicken pox), yellow fever, rabies, *Bacillus Calmette-Guérin (BCG)*, and typhoid vaccine. Seasonal influenza vaccines for injection are generally killed virus vaccines and are allowed; however, intranasal influenza vaccines (eg, *FluMist®*) are live attenuated vaccines and are not allowed.
6. History of immunodeficiency or receiving chronic systemic steroid therapy (in dosing exceeding 10 mg daily of prednisone equivalent) or any other form of immunosuppressive therapy within 7 days prior to the first dose of study drug.

RESOLVE	C/43/2022	Imperial College London	v2.0 10 th July 2023
---------	-----------	-------------------------	------------------------------------

7. Active autoimmune disease that has required systemic treatment in the past 2 years (i.e. with use of disease modifying agents, corticosteroids or immunosuppressive drugs). Replacement therapy (eg., thyroxine, insulin, or physiologic corticosteroid replacement therapy for adrenal or pituitary insufficiency, etc.) is not considered a form of systemic treatment and is allowed.
8. History of (non-infectious) pneumonitis that required steroids or has current pneumonitis.
9. History of Human Immunodeficiency Virus (HIV) infection.
10. Has a known history of Hepatitis B (defined as Hepatitis B surface antigen [HBsAg] reactive) or known active Hepatitis C virus (defined as HCV RNA [qualitative] is detected) infection. Note: no testing for Hepatitis B and Hepatitis C is required unless mandated by local health authority.
11. History of active TB (Bacillus Tuberculosis).
12. History or current evidence of any condition, therapy, or laboratory abnormality that might confound the results of the study, interfere with the subject's participation for the full duration of the study, or is not in the best interest of the subject to participate, in the opinion of the treating investigator.
13. History of allogenic tissue/solid organ transplant.

RESOLVE	C/43/2022	Imperial College London	v2.0 10 th July 2023
---------	-----------	-------------------------	------------------------------------

5. PROCEDURES AND MEASUREMENTS

5.1 Identification and recruitment of participants

Patients diagnosed with GTD are routinely registered at one of two centres covering England and Wales: Charing Cross Hospital, London (CXH) and Weston Park Hospital, Sheffield. Patients with a diagnosis of CHM following primary evacuation of intrauterine disease registered at CXH will be identified and sent information about the trial to provide time to consider participation. Following primary diagnosis, patients routinely undergo hCG monitoring (2-weekly urine and blood until hCG normalisation and then monthly urine hCG). In approximately 10-15% of cases a rise or plateau in hCG occurs, indicating failure of primary evacuation resulting in development of postmolar GTN and the need for further therapy. At this point, patients are routinely invited to CXH for further evaluation and can be enrolled into the study.

5.2 Pre-screening

As part of routine evaluation of suspected postmolar GTN, patients undergo assessments to determine whether the disease is low or high risk based on the FIGO 2000 international guidelines. These tests include:

- Thoracic x-ray,
- Uterine ultrasound scan of the uterus
- Blood tests to determine hCG level, organ function and viral status.

Whilst low risk patients would be considered for single agent chemotherapy with methotrexate or second evacuation, high risk patients start multiagent chemotherapy.

All patients in this cohort will have elevated hCG due to the nature of the disease and hCG is a marker that is also elevated during pregnancy. To rule pregnancy out, blood hCG testing will be paired with an uterine ultrasound scan to confirm presence of cancer and absence of a foetus.

To reduce the number of patients we unnecessarily approach with further study information (which has the risk of increasing anxiety around the decision making process), we will offer the trial only to patients we have established to have low-risk disease amenable to second evacuation after the above standard of care investigations have been completed.

5.3 On Study Screening (pre-randomisation)

Pre-screening test results remain valid for 7 days prior to randomisation. Patients who are considered eligible based on pre-screening results will be invited to provide written informed consent before further study screening procedures.

RESOLVE	C/43/2022	Imperial College London	v2.0 10 th July 2023
---------	-----------	-------------------------	---------------------------------

We will obtain consent followed by on study screening procedures commencing on the day of attending CXH. These processes are expedited for the following reasons: firstly, to minimise the time between diagnosis and definitive therapy since delays introduce additional risks; secondly, as a national service, patients may travel long distances to attend CXH and we aim to reduce the inconvenience of additional attendances.

Data obtained as standard of care prior to written informed consent may be used for the study provided they comply with the protocol specified timelines.

Once written informed consent has been obtained, patients will be added to the study database, where a unique Screening ID will be allocated. This should be used in all correspondence during the screening period.

Screening procedures and assessments are as follows:

- Collection of demographic data
- Review of medical history to include cancer history and treatment
- Physical examination and performance status
- Blood tests to confirm eligibility: thyroid function test, cortisol.
- Record of vital signs (including height and weight)
- Assessment of concomitant medications
- Collection of research bloods
- Recording of blood test results done as part of pre-screening: renal/liver function, full blood count, viral screen, coagulation screen, hCG
- Recording of ultrasound scan and chest x-ray results done as part of pre-screening

A complete record of all patients who enter screening for the study, and those who go on to be enrolled, must be maintained at each site. The site investigators are responsible for ensuring that this record includes the allocated ID as well as the patient identifiable data including name, hospital number and date of birth.

Eligible patients who take part in the study must meet all the listed inclusion criteria and none of the exclusion criteria (section 4.1).

